1.5 Summary of Pioglitazone pharmacological and toxicological data: Pioglitazone was FDA approved in 1999 to improve glycemic control in patients with type 2 diabetes, thus side effects and risks are well known. The FDA package insert provides information on a variety of risks and potential side effects that is summarized: The most common side effects (>5%) include upper respiratory tract infection, pharyngitis, headache, sinusitis and myalgia. Although the overall risks of these problems are greater than 5%, the risks when compared to placebo are all less than 5%. Of note, there have also been several warnings issued regarding pioglitazone. First, pioglitazone alone or more commonly in combination with other antidiabetic agents (typically insulin) can cause fluid retention and edema which increases the risk of congestive heart failure. The risk of heart failure was more common when comparing pioglitazone to placebo in a high-risk group of patients with diabetes and pre-existing cardiovascular disease (44). There have been several reports of hepatotoxicity but not enough data to establish probable causality. There was a small increased rate of fractures in women and a small increased risk of urinary bladder cancer in patients treated for 24 months or longer. Finally, pioglitazone is a category C medication and thus should not be used in pregnancy and it may also induce ovulation so individuals may be at greater risk for pregnancy when taking this medication (45).

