3.0 Research Design and Methods

3.1 Overview

This proposed research study is a double-blind controlled clinical trial of 200 Veterans with AUD randomized to either pioglitazone or placebo.

After screening visits and informed consent, participants who meet all inclusion and exclusion criteria and who sign the informed consent will be given a breathalyzer test and test result must be below 0.05 in order for potential participant to be enrolled (see Breathalyzer Testing section, precautions will be taken based on test result). Following the breathalyzer test, participants will complete the initial assessment instruments, which include the SCID, Obsessive Compulsive Drinking Scale (OCDS), Timeline Follow Back (TLFB), Beck Depression Inventory-2nd edition (BDI-II) and the PTSD Checklist (PCL-5). They will also provide a urine sample for a urine drug screen, Ethyl Glucuronide (EtG), and Ethyl Sulfate (EtS), and blood samples for ALT, AST and BNP. Women of childbearing potential will provide a urine sample for Beta-Human chorionic gonadotropin (β -HCG). Participants will then be randomized to receive either pioglitazone or a placebo (see **Data Analysis Plan-Randomization** section).

After randomization, all the participants will be seen weekly for the first 4 weeks (visits 1,2,3,4- baseline or randomization visit will be visit 0) then every 2 weeks until the end of the study (week 6 or visit 5, week 8 or visit 6, week 10 or visit 7, week 12 or visit 8, and week 14 or visit 9) for a maximum of 12 visits (including the screening visit, baseline visit, and closeout visit). At week 16, there will be a termination or closeout visit after study medications have been tapered. All study measures will be administered at each visit during the double-blind period from weeks 0 to 14 and week 16 or the closeout visit. In particular, the BDI-II and PCL-5, will be given at each study visit. If participants report significant depressive or other psychiatric symptoms during the study, the decision to exclude them will be based on whether they can safely participate in the remainder of the study (See **Human Subjects** section). Data will also be collected from participants' medical records regarding enrollment and attendance at specialty alcohol treatment appointments. Follow-up assessments will be conducted in person by a rater blinded to the participant's study condition.

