The initial screening and baseline visit (may be done at the same time) and week 4 and 14 visits will be conducted in person. However, to enhance subject safety and minimize the risk of COVID-19, all other visits will be conducted by phone but may be conducted in person if the patient requests or if in the opinion of the PI a face-to-face visit is necessary for subject safety.

Participants will have medication adherence assessed at each study visit (total number of tablets dispensed – tablets reported taken divided by the total number of tablets dispensed taking into consideration that patients will be given additional study medication in the event of missed visits- 7 days of additional medication). Tablet counts will be confirmed at each of the face-to-face visits. Participants will have a breathalyzer test at each face-to-face visit and will not be allowed to complete assessments if their test result is above 0.05%. For phone visits, subjects will be evaluated clinically for intoxication ie coherent speech, slurred words, able to follow questions and respond appropriately.

Measure	Week	May occur at same visit		Double Blind Period										
		Screening	Baseline	Week 1	Week 2	Week 3	Week 4	Week 6	Week 8	Week 10	Week 12	Week 14	Week 16	
Informed Consent		X	X											
Eligibility Determination		X												

SCID DSM-5	X										
Randomization (pioglitazone or placebo)		X									
Demographics/ Medical History	X										
Pharmacy Dispenses Study Drug (pioglitazone or placebo)		X	X	X	X	X	X	X	X	X	
Determination of Study Drug Compliance			X	X	X	X	X	X	X	X	X
BBCET		X	X	X	X	X	X	X	X	X	
Breathalyzer	X	X	X	X	X	X	X	X	X	X	X
BSI		X	X	X	X	X	X	X	X	X	X
BDI-II		X	X	X	X	X	X	X	X	X	X
PCL-5		X	X	X	X	X	X	X	X	X	X
OCDS		X	X	X	X	X	X	X	X	X	X
TLFB	X	X	X	X	X	X	X	X	X	X	X
EtG/EtS, (Urine)		X				X					X
ALT, AST, GGTP, BNP, CK		X				X					X
CRP		X				X					X
Inflammatory markers		X				X					X
Medication side effects			X	X	X	X	X	X	X	X	X
Attendance at EtOH Tx	X		X	X	X	X	X	X	X	X	X
Urine Drug Screen, β - HCG	X										

Participants will provide a urine sample for EtG, EtS, and β -HCG (for women of childbearing potential), ALT, AST, GGTP, CK and BNP at baseline. The EtG, EtS, ALT, AST, GGTP and BNP, will be repeated at weeks 4, and 14.

3.2 Participants: Male and female Veterans above the age of 18 will be recruited from outpatient clinics at the Minneapolis and Long Beach VAHCS's and through advertisements at each site.

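### Urine β-HCG is scheduled at entry only, with no planned pregnancy test during 14 weeks of dosing plus taper, despite the protocol's own pregnancy and ovulation warning

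*Combined protocol and SAP*

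**What the plan says.** Section 1.5 gives the warning in two parts. The first concerns use of the drug by a pregnant woman: "pioglitazone is a category C medication and thus should not be used in pregnancy". The second concerns the chance of conceiving during treatment: "it may also induce ovulation so individuals may be at greater risk for pregnancy when taking this medication".

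The supplied text provides for the pregnancy test in these places, all at entry:

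- The narrative in 3.1 puts a urine β-HCG for women of childbearing potential among the initial assessments. The next step is "Participants will then be randomized to receive either pioglitazone or a placebo".
- The schedule table in 3.1 has a shared row, "Urine Drug Screen, β - HCG", with a single mark.
- The text under the table places β-HCG at baseline, then says of later testing: "The EtG, EtS, ALT, AST, GGTP and BNP, will be repeated at weeks 4, and 14".
- Inclusion criterion 6 (3.4) requires a negative test.

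Exclusions 8 and 10 (3.5) rule out women who are pregnant, planning pregnancy or nursing, and women unwilling to use barrier contraception.

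After entry, 3.1 says that "week 4 and 14 visits will be conducted in person", whereas "all other visits will be conducted by phone but may be conducted in person if the patient requests"; the same sentence also lets the PI call a participant in for safety. Medication side effects are recorded at each post-baseline visit, and 3.11 sends concerning ones, and laboratory abnormalities, to the PI or site PI. Drug continues to week 14 and is then tapered, with closeout at week 16 (3.1, 4.4).

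**The concern.** On the protocol's own account, the drug may raise the chance of the very event in which it should be avoided. That risk begins with dosing, so a negative result at entry cannot address it. If a woman conceives on drug, no planned test would show it, and she could go on taking a dose titrated to 45 mg per day until she or someone else suspected the pregnancy. Most contacts in that period are by phone. The stake is participant safety; no estimate or test in the analysis plan depends on it.

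**Working it through.** There is no stated figure to reproduce. The check is a count from 3.1 and 3.7, followed by a reading of the sentences that might supply a later test.

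**Counts**

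- Planned β-HCG after first dispensing: 0. Drug exposure: weeks 0 to 14, plus a taper complete by week 16.
- Post-baseline visits: weeks 1, 2, 3, 4, 6, 8, 10, 12, 14, 16 = 10. In person: weeks 4 and 14 = 2. Planned by phone: 10 − 2 = 8.
- Dispensings (3.7): baseline and weeks 1, 2, 3 = 4; weeks 4, 6, 8, 10, 12 = 5; total 4 + 5 = 9. After the entry visit: 9 − 1 = 8. Only week 4 of these is in person, so 8 − 1 = 7 fall at visits planned by phone.

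**Does any other sentence schedule a later test?**

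- The repeat list under the table omits β-HCG. That alone proves little, since it also omits CK, CRP and the inflammatory markers, which the table does mark at weeks 4 and 14. For β-HCG the table offers no later mark either.
- Section 3.1 also says "All study measures will be administered at each visit during the double-blind period from weeks 0 to 14". Read literally, this would include β-HCG. But the table and the text under it confine the blood tests and EtG/EtS to baseline, week 4 and week 14, and a urine test cannot be done at a phone visit. The specific schedule has to govern.
- Section 3.9.2 repeats the urine drug screen at all follow-ups. β-HCG shares its table row, but the sentence names only the drug screen.
- Section 3.11 stops drug after three consecutive missed visits, or for serious adverse effects that require unblinding. Pregnancy is not mentioned.

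**Effect of the change**

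- Tests at weeks 4 and 14: 1 + 2 = 3 in all. The week-4 result would come before 5 of the 9 dispensings.
- Longest stretch without a test, up to week 14: 14 weeks now; 14 − 4 = 10 weeks with a week-4 test. One added test is therefore not enough by itself.
- A question at every post-baseline visit is asked at intervals of at most 2 weeks if visits are kept, which covers weeks 4 to 14.

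**The case against.** The strongest objection is that absence is not established. Section 3.1 refers to a Human Subjects section that was not supplied, and pregnancy handling could be set out there. A reader might infer that the trial has no pregnancy monitoring on treatment; the documents support only that the supplied schedule shows none. This stands, and the fix is conditional on it.

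The risk is also already reduced. Entrants must test negative, must not be planning pregnancy and must accept barrier contraception. Side effects are reviewed at each visit, and the PI can bring a participant in. About half would be on placebo. All of this is fair, and it limits the severity. But the entry criteria detect nothing later, and a for-cause visit needs a report or a suspicion first.

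Two stronger arguments are tempting and do not hold:

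- A reader might infer that β-HCG is singled out as the one laboratory item never repeated. That requires following 3.9.2 over the table for the drug screen while following the same table row for β-HCG. If the table governs both, the drug screen is not repeated either.
- A reader might measure the gap by the share of drug supply released after week 4. The supplies in 3.7 overlap to allow for missed visits, so supply is not exposure.

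The table's entry mark appears to sit under Screening while the text says baseline. This is minor: columns were damaged in extraction, the two visits may coincide, and the text already puts the test at baseline before randomization.

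**Conclusion.** The point holds as a low-to-moderate safety improvement. In the supplied text β-HCG is planned once at entry and not again over 14 weeks of dosing plus taper, for a drug that section 1.5 warns about on both pregnancy and ovulation. Existing safeguards reduce the risk, but detection during treatment depends on self-report or suspicion.

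This rests on two conditions: that the Human Subjects section contains no on-treatment testing, and that the specific schedule overrides the general sentence on measures at each visit. The number of women of childbearing potential is not stated, so the number of participants affected cannot be given. Sample size, alpha, power and the primary comparison are untouched.

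**What to change.** First check the Human Subjects section. If it does not already provide the following, add for women of childbearing potential:

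1. Urine β-HCG at week 4, on the sample already collected in person, read before that visit's drug is dispensed; and again at the in-person week-14 visit, before the taper starts. Give β-HCG its own table row so that these marks are unambiguous.
2. As a core part of the change, a question on a missed period or contraception lapse at every visit, phone visits included, with an in-person test if the answer is yes. Section 3.9.1 says the side-effect checklist is still to be developed, so the question can be built in.
3. A sentence in 3.11 stating that study drug stops on a positive test while follow-up data are still collected, in line with what 3.11 already intends after a stop.

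Apply this in both arms so that the blind is kept. The cost is about two urine strips per woman of childbearing potential, an occasional confirmatory test or extra in-person visit, and a possible short interruption of drug after a false positive. It adds no routine visit and no staff.

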3.6 Feasibility

Currently, the Minneapolis VAHCS serves approximately 100,000 unique Veterans and 9,550 were diagnosed with an AUD. At the Long Beach VAHCS approximately 60,000 unique Veterans are seen each year and nearly 5,425 received a diagnosis of AUD. Furthermore, each site has a long history of research of AUD and a strong collaboration between researchers and clinical staff at each site. We have also collaborated on several similar studies and have experience in recruiting and maintaining participants with similar characteristics from our work on two prior CSR&D funded RCT's, "Efficacy & safety of baclofen to reduce alcohol use in veterans with HCV" and "Motivating Chronic Hepatitis C patients to Reduce Alcohol Use". In these studies we successfully recruited 180 subjects with AUD and hepatitis C (a much smaller subgroup of all Veterans with AUD) during the course of the studies. Thus, we expect to be able to easily meet our recruitment goal of 200 subjects during the 4 year study. Finally, we have

already received an Investigational New Drug exemption for pioglitazone (see attachment) so this will not be a barrier to starting the study.

3.7 Intervention

At the baseline (week 0) visit participants will be randomized to receive either pioglitazone or a matching placebo by the research pharmacist (**see Randomization section**). Participants and study personnel will be unaware of the treatment assignment. In order to maintain study blind but insure patient safety, sealed envelopes that contain the identification of the study medication (pioglitazone or placebo) will be kept in the research pharmacy and opened only in case of emergency. Study medication will be dispensed in a double-blind fashion during the entire study period. Study medication will be dispensed at baseline and weeks 1,2 and 3 sufficient for a 2-week period (taking into consideration the possibility of missed visits) and will be given at weeks 4,6,8,10, and 12 sufficient for a 3-week period (taking into consideration the possibility of missed visits). Placebo capsules will be of an identical size, shape and color as pioglitazone. Active medication will be started at 15mg per day and titrated over two weeks until reaching a target dose of 45mg per day. This is the FDA maximum dose and was selected based on a prior small study focused on the treatment of cocaine use (43).

All participants will receive Brief Behavioral Compliance Enhancement Treatment (BBCET) as their psychosocial treatment. This is a standardized 15-minute intervention that emphasizes medication adherence as a crucial element to change alcohol use behavior (56). It will be administered at every visit. BBCET has been used in previous AUD medication trials as the psychosocial treatment (27, 57). We also used the BBCET for the CSR&D funded “Efficacy & safety of baclofen to reduce alcohol use in veterans with HCV” and have extensive knowledge in delivering this intervention (34). Study staff will be trained to administer the BBCET and 2% of sessions will be observed for adherence to the intervention.

3.8 Compensation

Participants will be compensated \$20 for completion of study questionnaires and providing urine and blood samples at the baseline visit and \$20 for completing each follow-up visit. If participants complete the data collection at all 11 time points they will receive a total of \$220.

3.9 Measures

Screen for current intoxication. Blood alcohol concentration (BAC) will be measured using the AlcoMate Revo Breathalyzer which measures BAC% between 0.00% and 0.400% in 0.01% steps. Sensor accuracy of the AlcoMate is +/- 0.02% BAC. This measure will be taken prior to any study related interactions with subjects to insure that they are not intoxicated at the time of evaluation. If a subject's BAC is above 0.04% scheduled tasks for that day will be rescheduled. If the subject is driving, alternative arrangements will be made for their transportation home.

3.9.1 Rating Scales

The Structured Clinical Interview for DSM-5 (SCID). The SCID will be used at the initial assessment to identify alcohol use disorder and other substance use disorder (58). All SCID interviewers will be trained by a qualified SCID trainer (including PI and CO-I's) and will

demonstrate competency in administering the SCID. Research has shown that this method for determining psychiatric diagnostic information is reliable and valid (59).

The Time Line Follow-Back (TLFB). The TLFB interview will be used to identify daily drinking patterns of subjects in the three months before treatment and the intervals between study assessments (60). The TLFB has been shown to have adequate psychometric qualities in both clinical and research populations (61). Using a calendar, the respondent provides retrospective estimates of daily alcohol drinking over a specified amount of time. All primary and secondary outcomes will be derived from the TLFB assessment including: 1) heavy drinking over the last 8 weeks of the study; 2) percent or number (depending on the distribution) days drinking per month; 3) number of drinks per drinking day; and 4) number of heavy drinking days per month (heavy drinking days defined as for men: >4 drinks in a day or women: >3 drinks in a day).

Beck Depression Inventory-2nd edition. The BDI-II is a 21-item self-report instrument that will be used to assess depressive symptomatology. Total score of 0-13 is considered minimal range, 14-19 is mild, 20-28 is moderate and 29-63 is severe symptoms. The BDI-II has been shown to have good validity and reliability in various psychiatric populations (62). The BDI-II will be administered at the initial and all follow-up assessments. The suicide ideation item will be reviewed at every visit prior to completion of visit and if positive will prompt a suicide risk assessment and further evaluation and/or referral for treatment.

Brief Symptom Inventory (BSI). The BSI is a 53-item self-report measure that will be used to assess several dimensions of psychopathology. The scale has nine primary symptom dimensions and three global indices. It is a reliable and valid instrument and has been normed to both adult non-patients as well as adult psychiatric patients (63). It will be administered at baseline and all follow-up assessments.

PTSD Checklist for DSM-5 (PCL-5). The PCL-5 is a brief 20-item self-report instrument that will be used to assess Post Traumatic Stress Disorder symptoms. Total score of 0-33 is considered not indicative of severe symptoms of PTSD, 34-80 is considered indicative of symptoms of PTSD. The PCL-5 has been shown to have good validity and reliability in various populations (64). The PCL-5 will be administered at the initial and all follow-up visits.

Medication Side-effect checklist: We will develop a side effect checklist to monitor any adverse effects from the medication. We will base the checklist on the package insert and data from prior studies, including the Schmitz et al study.

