In addition to the package insert there are a variety of published data in a diverse number of conditions including four published reports in patients treated for depression and a recent study that used pioglitazone to treat cocaine use which included 26 individuals with alcohol use disorder- see above. Studies with important safety information are summarized here: A meta-analysis of pioglitazone used for reducing liver fibrosis in nonalcoholic steatohepatitis reviewed 8 RCT's with 516 patients followed between 6 and 24 months and found weight gain and lower limb edema as the primary adverse events (46). A recently published article using pioglitazone, for 30 months, in a similar clinical population, found no difference of major drug-related adverse events with minimal weight gain being the primary difference between pioglitazone and placebo (47). Although prior retrospective studies led to the FDA boxed warning for bladder cancer, two recent prospective studies suggest no link between pioglitazone and bladder cancer (48, 49). There have been four published RCT's of pioglitazone for major depressive disorder with a total of 161 patients enrolled (6-12 week studies) with no significant adverse events occurring (50-53). Pioglitazone has also been explored as a treatment for dementia. A recent meta-analysis using PPAR- γ agonists to treat dementia found 9 studies in 4,327 participants and found no significant difference in adverse or serious adverse events (54). A recent placebo controlled trial of pioglitazone for 30 patients with cocaine use disorder of whom 26 had an AUD reported the most frequent side effects were sleep disruption, diarrhea, stomach pain, cough, and increased urination which were all rated as mild (43). Finally, a recent, very small randomized trial comparing pioglitazone to placebo in a "mechanistic proof of principle" study to determine the effect of pioglitazone on alcohol craving was stopped early after 16 subjects were randomized due to safety concerns. The study entailed two experimental manipulations designed to induce alcohol craving, guided imagery compared to intravenous lipopolysaccharide. A total of 14 subjects (6 pioglitazone and 8 placebo) were analyzed. Five in the pioglitazone arm had elevated creatine kinase (CK), one was deemed serious and one receiving placebo had an elevated CK. The study did not report absolute values for CK nor whether or how the CK was related to the initiation of pioglitazone or other whether it was temporally related to other study procedures (Schwandt et al psychopharmacology 2020). **In summary, pioglitazone is well tolerated with few side effects or significant safety concerns, particularly in short term (less than 24 weeks) studies.**

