3.9.4 Inflammatory Markers

C-Reactive protein (CRP): is a protein found in the blood plasma that rises in response to inflammation. CRP will be assessed to check inflammatory responses to pioglitazone. Other inflammatory markers such as interleukin-6,8 and 12 as well as tumor necrosis factor- alpha and SB100 a marker of blood brain barrier inflammation will be tested. One of pioglitazone's purported mechanism of action is via inflammation thus we will test for these markers.

3.10 Potential hazards to personnel and precautions: Collection of blood and urine samples may pose a hazard to study personnel. Contact with blood or urine has the potential to transmit disease. The collection of blood will be performed in the existing Minneapolis and Long Beach VAHCS laboratories where lab technicians are already trained and utilize universal precautions. The collection of urine samples will be completed in the clinics by research staff. All staff will be trained in universal precautions and the study will comply with all safety regulations and training stipulated by VA.

3.11 Follow-up: At each visit, research coordinators will administer all measures, dispense medication and deliver the BBCET. Any concerning side effects or lab abnormalities will be reviewed with the PI or site PI. Appropriate medical evaluation will be undertaken as deemed necessary by the PI's. Subjects who miss three consecutive visits will stop the medication as they will have been off of medication for minimum of 1 week. Any serious adverse side effects where the blind needs to be broken will result in stopping the assigned treatment. However, every effort will be made to gather research data through the end of the study.

3.12 Randomization: Participants will be randomly assigned to one of two groups (pioglitazone or control/ placebo) using a minimization method of Pocock and Simon (1975)(68). Randomization will be stratified by site (Minneapolis and Long Beach) and will be handled centrally by the Data Coordinating Center at the Minneapolis VA, and a special randomization program will be developed in consultation with a statistician in Minneapolis ([name]). The program will track the balance of stratification variables (i.e., site) for each condition and change the probability of assignment if the variables are unbalanced. This method assures that the two groups are comparable with respect to the stratification variables throughout the study period.

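### The visit schedule starts the side-effect checklist at week 1 although the text says all measures begin at week 0, and no body-weight measurement appears in the schedule or section 3.9.

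*Combined protocol and SAP*

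**What the plan says.** **Checklist.** Section 3.9.1 describes an instrument still to be written: "We will develop a side effect checklist to monitor any adverse effects from the medication". On content it adds only this: "We will base the checklist on the package insert and data from prior studies". It gives no items and no visit times. By contrast, the entries for the BDI-II, BSI and PCL-5 each state that the scale is given at the initial or baseline assessment and at follow-up.

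**Schedule.** In the section 3.1 table, the row "Medication side effects" is empty under screening and baseline. It is marked at weeks 1, 2, 3, 4, 6, 8, 10, 12 and 14.

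**General text.** Section 3.1 states: "All study measures will be administered at each visit during the double-blind period from weeks 0 to 14 and week 16 or the closeout visit". Section 3.11 states: "At each visit, research coordinators will administer all measures, dispense medication and deliver the BBCET". Read literally, the first of these includes week 0.

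**Weight.** Section 1.5 reports a meta-analysis of eight randomized trials that "found weight gain and lower limb edema as the primary adverse events". It also reports a 30-month study in which weight gain, described as minimal, was the main difference from placebo. Neither the schedule nor section 3.9 lists weight, BMI or vital signs. By default only screening/baseline, week 4 and week 14 are in person; the other visits are by phone.

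**The concern.** Many of the effects that section 1.5 leads one to expect are non-specific: headache, myalgia, sleep disruption, diarrhea, stomach pain. Heavy drinkers may plausibly have some of these before any dose. Without a pre-dose checklist, a symptom reported at week 1 cannot reliably be identified, item by item, as new, worse or unchanged. Safety tables would then have to report symptoms present at any time rather than treatment-emergent symptoms.

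Weight raises a related problem. The background presents weight gain as a principal adverse effect of the drug. Without a measured baseline and follow-up weight, the trial could not report mean weight change by arm. Any information would come from checklist items not yet written, answered mostly by phone.

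Tolerability is part of the protocol's argument for repurposing pioglitazone, so both gaps bear on what the trial can report. Neither touches the primary or secondary drinking outcomes in section 4.4. A baseline not taken before the first dose cannot be recovered afterwards.

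**Working it through.** The plan states no figure on this point, so there is nothing to reproduce. The check has three parts.

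**1. Is the table being read correctly?** The table was extracted from a PDF, so column alignment needs confirming. Two other rows serve as tests.

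- The ALT/AST/GGTP/BNP/CK row, with the same column mapping, falls at baseline, week 4 and week 14. The text below the table agrees: "The EtG, EtS, ALT, AST, GGTP and BNP, will be repeated at weeks 4, and 14".
- The dispensing row runs from baseline to week 12, matching section 3.7.

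Under that mapping the side-effect row has 9 marks, starting at week 1. The BSI, BDI-II, PCL-5 and OCDS rows have 10, starting at baseline. The side-effect row has the same pattern as study-drug compliance, which can only start after dosing. The week 16 column cannot be read reliably, but that does not affect the baseline question.

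**2. Table or text?** The all-measures sentence is not literally true of every measure: the laboratory tests are scheduled three times and the SCID once. The row-specific table is therefore the better guide to what sites would do, but the documents do not settle it.

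**3. What would a missing baseline cost?** This is an illustration. The symptom rates are assumptions, not document figures.

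Inputs:
- New onset among those symptom-free at baseline: 10% on placebo, 25% on pioglitazone (assumed).
- Share b already symptomatic in each arm: 0 to 40% (assumed). These participants report the symptom during follow-up whichever arm they are in.
- n per arm: 100 (200 participants, section 3.1, assumed split equally), or 80 after the 20% attrition in section 4.6.
- Alpha 0.05 (section 4.4), taken as two-sided.

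Formulas:
- Without a baseline, the proportion ever reporting is p = b + (1 − b) × new-onset rate, with n per arm.
- With a baseline, the new-onset rates are compared directly, with n(1 − b) per arm.
- Power = Φ[(d − 1.96·se0)/se1], where d is the difference, se0 the pooled standard error and se1 the unpooled one.

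Worked case, n = 100 and b = 20%:
- Without: p = 0.20 + 0.80 × 0.10 = 0.28 and 0.20 + 0.80 × 0.25 = 0.40, so d = 0.12. With se0 = 0.0670 and se1 = 0.0665, (0.12 − 0.1313)/0.0665 = −0.17, giving power 43%.
- With: 10% v 25%, 80 per arm, d = 0.15. With se0 = 0.0601 and se1 = 0.0589, (0.15 − 0.1178)/0.0589 = 0.55, giving power 71%.

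| Already symptomatic | Ever reported, placebo v drug | n = 100: without / with baseline | n = 80: without / with baseline |
|---|---|---|---|
| 0% | 10% v 25% | 80% / 80% | 71% / 71% |
| 10% | 19% v 32.5% | 59% / 76% | 50% / 66% |
| 20% | 28% v 40% | 43% / 71% | 36% / 61% |
| 40% | 46% v 55% | 25% / 58% | 21% / 49% |

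The 12-point gap in the worked case is exactly 0.80 × 15 points, the true absolute excess across the whole arm. The estimate is therefore not biased; the loss is in precision.

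**Weight.** Weeks 1, 2, 3, 6, 8, 10 and 12 are phone visits by default, so 7 of the 9 side-effect assessments are remote. No weight is scheduled at baseline, week 4 or week 14. No precision can be computed for weight change because the documents give no standard deviation.

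**The case against.** The strongest counter-case has five parts.

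- *The text may already provide a baseline.* Sections 3.1 and 3.11 say all measures are given at each visit, including week 0. This stands to the extent that the finding is a conflict, not a proven omission. The list of initial instruments in section 3.1 settles nothing: it leaves out the checklist, but it also leaves out the BSI, which is certainly given at baseline.
- *Randomization protects the comparison.* This stands. A reader might infer that a missing baseline hides a true excess on pioglitazone. It does not: pre-existing symptoms are balanced in expectation and the prevalence difference is unbiased.
- *Some pre-treatment information exists.* Medical history is taken at screening; psychiatric scales and laboratory tests, including CK, are taken at baseline. The unwritten checklist could also ask about onset or change. This is partial cover, but it does not give an item-by-item baseline for the listed symptoms.
- *Fluid retention is not left to self-report.* Clinically significant edema is excluded at entry, BNP is measured at baseline and weeks 4 and 14, and concerning side effects go to the investigator for medical evaluation. This stands for fluid retention in part, but none of it measures weight.
- *The weight evidence comes from longer studies.* The trials in the meta-analysis followed patients for 6 to 24 months and the other study ran for 30 months, with only minimal gain; this trial's double-blind period is 14 weeks. The cocaine-use study in section 1.5, the closest population cited, does not list weight gain among its most frequent effects. This lowers the expected size of any weight effect, but does not remove the value of measuring it.

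**Conclusion.** The point holds as a cheap improvement. The schedule and the text disagree on whether the side-effect checklist is given before the first dose, and the documents supplied plan no objective weight measurement in the schedule or section 3.9.

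If the table is followed, the loss is reliable treatment-emergent classification, plus precision. Under the assumed 10% v 25% new-onset rates with 100 per arm, power falls from 76% to 59% when 10% are already symptomatic, from 71% to 43% at 20%, and from 58% to 25% at 40%. These figures assume a 15-point effect. Section 1.5 puts the placebo differences for the common labelled effects below 5%, so power for those would be lower with or without a baseline. The table shows the direction and relative size of the loss, not a forecast.

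Two stronger readings are not supported. One is that the trial could not distinguish drug effects from pre-existing symptoms at all; the placebo arm still allows an unbiased comparison of prevalence. The other is that weight is never measured; section 3.1 refers to a Human Subjects section that is not in the document supplied, so the claim reaches only as far as the schedule and section 3.9.

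**What to change.** 1. Reconcile the section 3.1 table with the all-measures statements in sections 3.1 and 3.11 by marking the checklist at baseline, completed once before the first dose. State its timing in section 3.9.1.
2. State in the analysis plan that side effects will be reported by arm as new or worse than baseline, with prevalence at any time alongside if wanted.
3. Add body weight to the schedule and to section 3.9 at baseline, week 4 and week 14, and report change from baseline by arm. If the Human Subjects section already provides for weight, cross-refer to it instead.

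The cost is one extra completion of an existing checklist and three weighings, a few minutes per participant. All three time points are already in person, so no extra visit or staff is needed.
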